### 10.5.7 Safety analysis

Safety will be analysed in the safety population, with all centres pooled. The statistical analysis will be mainly descriptive. For qualitative variables, 95% CI of percentages will be computed, and for quantitative variables, 95% CI of means will be computed.

## ALLOB-DU1 - Clinical Study Protocol

ALLOB-DU1\_CSP

V 05

Author: [name]

February 02, 2017

Pg. 101/136

10.5.7.1 *AEs and SAEs*

AEs and SAEs will be coded using the Medical Dictionary for Regulatory Activities (MedDRA). For each AE reported, the number and percentage of patients will be tabulated based on system organ class and preferred term. Similar tabulations will be performed by severity, relationship to the study product/procedure, action taken and outcome. The number and percentage of patients who experienced an AE as defined in the pre-defined subsets of events will also be tabulated.

The frequency of AEs and SAEs will be estimated by using the 95% CI.

An analysis of following parameters will also be performed:

- Treatment-emergent (S)AE (occurring or worsening after ALLOB® implantation)
- (S)AE leading to premature withdrawal

10.5.7.2 *Other safety variables*

For blood pressure, standard summary statistics will be provided at baseline and each follow-up visit, including mean values and mean changes from baseline. Heart rate measurements will be summarised for the mean values and the mean changes from baseline at each follow-up visit using standard summary statistics. Shift tables [low (<50 bpm), normal (between 50 bpm and 120 bpm), and high (>120 bpm)] showing each individual patient's baseline value and follow-up visits will be performed.

[REDACTED]

[REDACTED]

[REDACTED]

Standard summary statistics of laboratory values and shift tables presenting incidence of laboratory abnormalities will also be provided. The frequency of normal / abnormal examination will be tabulated for each time point.

Detailed statistical methodology for the safety analyses will be provided in the SAP.

## ALLOB-DU1 - Clinical Study Protocol

ALLOB-DU1\_CSP

V 05

Author: [name]

February 02, 2017

Pg. 102/136

10.5.8 Interim data analysis10.5.8.1 *Efficacy Assessment*

At Month 6, the efficacy assessment will be based on:

- The patient had a rescue surgery

Or

- The Global Disease Evaluation score (VAS) as perceived by the patient has not improved by at least 25% *and* the TUS as assessed by CT scan has not increased by at least 2 points (versus baseline).

For rescue surgery, based on the efficacy of the treatment, Investigators will have the opportunity to switch to rescue surgery from Month 3 if the patient has not improved by at least 15% his/her global disease evaluation score (VAS) as perceived by the patient and his/her mRUS or TUS, as available, has not improved by 1 point.

The levels of improvements have been calculated as based on other similar impaired fracture healing trials (e.g., PREOB® on non-union fracture) and take into account standard deviation and patient variability.

10.5.8.2 *Presentation of the 2-stage design*

The main objective of this phase I/II-a non-comparative sequential design is to assess the interest presented by this new treatment without performing a comparative study that allows identifying only small differences of efficacy between the new treatment and a control, what requires a relatively high number of subjects. The principle of a sequential design is to perform the study in two or more stages in order to minimize the number of patients exposed to an ineffective treatment to conclude in a more premature way.

The most appropriate sequential method for this study is the 2-stage Fleming plan. In this design, the efficacy criterion is a binary criteria of “success/failure” type, with  $p_0$  as the superior limit of ineffectiveness (maximum value below which the new treatment is considered as being ineffective) and  $p_1$  as the inferior limit of efficacy (minimum value above which the new treatment is considered as being effective). The null and alternative test hypotheses are the following:

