**Detailed visit schedule**

After informed consent is obtained, fulfilment of study inclusion and exclusion criteria will be performed at Visit #1, which will take up to 8 weeks to complete. Visit #2 is scheduled to take place after completion of Visit #1 for baseline clinical assessments and ALLOB® implantation (the baseline of the radiological assessments is Visit #1). At Visit #2, all patients will be hospitalized for 24 or 48 hours after implantation, according to the judgment of the Investigator.

Patients will be followed during 6 months, at 2 weeks, 1, 3, and 6 months (Visit #3 to Visit #6).

[REDACTED]

[REDACTED]

[REDACTED]

[REDACTED]

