## 1 INTRODUCTION

### 1.1 General Background

#### 1.1.1 Impaired Fracture Healing

Bone has a substantial capacity for repair and regeneration in response to injury or surgical treatment. Both processes involve a complex integration of cells, growth factors and extracellular matrix. Repair simply restores the continuity of the injured tissues without necessarily increasing bone volume, while regeneration involves the differentiation of new cells and the formation of new bone tissue, which results in an overall increase in the volume of new skeletal tissues. Fracture healing is a multistage repair process that involves complex well-orchestrated steps that are initiated in response to injury, resulting eventually in the repair and restoration of function (Al-Aql *et al.*, 2008).

Fractures are now successfully treated in the majority of patients; nevertheless about a third requires some surgical intervention. Among those, delayed-unions or non-unions may necessitate numerous operative procedures, can leave the patient with functional deficits, and are often associated with prolonged morbidity (Wiss and Stetson, 1996).

Fracture healing is considered as a dynamic progressive process. Nowadays, intervention is usually indicated by 3 to 5 months after injury if monthly radiographic studies do not show progression of fracture healing (Wiss and Stetson, 1996).

Typically, delayed-union is a term used for a fracture that has not united within a period of time that would be considered adequate for bone healing. Delayed-union suggests that union is slow but will eventually occur without additional surgical or non-surgical intervention, whereas non-union is defined as the cessation of all reparative process of healing. There is no universally accepted or validated approach to evaluate the progression of fracture healing: definitions of delayed-union or non-union continue to be subject of various interpretations (Bhandari, 2002; Bhandari *et al.*, 2012). The distinction between delayed-union and non-union is based on time: a fracture not healed 3 to 8 months after onset is defined as a delayed-union, whereas a fracture not healed 9 months after onset is defined as non-union (regulatory definition).

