### **3.2.3 Rationale for the Choice of Clinical and Radiological Improvement Levels**

In their daily practice, orthopaedic surgeons take the decision of a new surgical intervention if signs of both clinical and radiological improvements are observed (i.e., signs of favourable evolution). This is because clinical and radiological improvements are not always correlated. This has been observed in other studies where some patients showed significant clinical improvement with limited radiological improvement or vice versa. In the present study, the same strategy of a combined clinical and radiological evaluation will help determining if a rescue surgery will be required or not.

Based on the efficacy of the treatment, Investigators will have the opportunity to switch to rescue surgery from Month 3 if the patient has not improved by at least 15% his/her global disease evaluation score (VAS) as perceived by the patient and his/her TUS or mRUS (as available) has not improved by at least 1 point.

The levels of improvements have been calculated as based on other similar impaired fracture healing trials (e.g., PREOB® on non-union fracture) and take into account standard deviation and patient variability.

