#### 10.5.1.2 *Type I error rate, significance tests*

In this study, two sided tests will be performed at a 5% level of significance except for efficacy analyses.

According to the Schoenfeld approach (Schoenfeld *et al.*, 1980), for the efficacy analysis, the type I error rate will be increased from the usual 5% to the 10% rate. Indeed, in this pilot single arm “proof of concept” study, it is appropriate to maintain the power and increase the type I error rate. This increases the risk of erroneously concluding that the treatment is worthy of further investigation, but does not increase the risk of missing an efficacious treatment. So in

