#### 10.5.8.3 Results of the computing

According to the 2 stages Fleming method, 20 treated patients are required (type I error rate  $\alpha$  of 5% and a statistical power of 80%). Taking into account that patients are enrolled by cohort of 4 and considering the potential heterogeneity of the population, 32 patients in total will be enrolled and treated in the study.

Step	Nb. of patients/step	Cumulated Nb. of patients	Treatment ineffective if $\Pi < 0.30$	Treatment effective if $\Pi > 0.70$
1	16 (assessable)	-	Number of successes $\leq 4$	Number of successes $\geq 12$
2	Up to 16 (assessable)	32	n.a.	n.a.

For the first 16 assessable patients, an interim analysis will be performed at the end of the 6 months follow-up (Visit #6).

The study will be prematurely stopped for:

- Safety concerns

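### Twelve successes in 16 does not by itself show that ALLOB is effective: the 30% null rate has no visible source, and the result rules out untreated success rates only up to about 51.6%

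*Combined protocol and SAP*

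**What the plan says.** Section 2.1 describes an open, uncontrolled, single-treatment study. Under Sections 10.2 and 10.5.6.1 a patient fails at Month 6 after rescue surgery, or if the GDE has not improved by 25% and the TUS has not risen by 2 points. Success is therefore no rescue plus either improvement.

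Section 10.5.8.2 introduces a two-stage Fleming plan. It defines p0 as the "maximum value below which the new treatment is considered as being ineffective", sets p0 = 0.30 and p1 = 0.70, and uses α = 0.05 and β = 0.20. Section 10.5.8.3 gives a type I error "of 5% and a statistical power of 80"%, asks for 20 treated patients, and stops for efficacy at 12 or more successes among the first 16 assessable patients. The table column for that limit is headed "Treatment effective if" Π > 0.70.

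Section 10.5.1.2 is more modest. It says that "the type I error rate will be increased from the usual 5% to the 10% rate" for efficacy, and describes the resulting risk as "erroneously concluding that the treatment is worthy of further investigation".

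Two other places bear on p0. Section 1.1.1 says: "Delayed-union suggests that union is slow but will eventually occur without additional surgical or non-surgical intervention". Section 3.2.3, repeated in 10.5.8.1, says: "The levels of improvements have been calculated as based on other similar impaired fracture healing trials (e.g., PREOB® on non-union fracture"). That sentence concerns the GDE and TUS cut-offs, not the 30% success rate.

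**The concern.** Without a control group, the comparison with p0 carries the whole efficacy inference. A positive result speaks about ALLOB only to the extent that untreated patients would have done worse. Here the reference value is stated without support, the endpoint can be met in either of two ways, and the protocol's background section allows for some spontaneous healing. The only response benchmark in the visible text, 75% to 85% in Section 1.1.6, is for autograft in treated non-unions and so cannot serve as an untreated rate.

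What is at stake is the claim made after 12 of 16. The step table would call the treatment effective, and Section 9.4 lists effectiveness as a reason to stop. Section 10.5.1.2 would call the same result grounds for further study.

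**Working it through.** **1. The plan's own figure.** Inputs from 10.5.8.2: p0 = 0.30, p1 = 0.70, one-sided α = 0.05 (since H0 is p ≤ p0), power 0.80. The single-stage normal approximation is

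N = [(z₀.₉₅√(p0q0) + z₀.₈₀√(p1q1)) / (p1 − p0)]² = [(1.645 + 0.842) × 0.458 / 0.40]² ≈ 8.1, so 9.

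The exact single-stage minimum is 10 (6 or more successes: α = 0.047, power 0.850). A two-stage Fleming plan of 6 + 6 gives α = 0.039 and power 0.859. The stated 20 is therefore not reproduced as a minimum, although 10 + 10 meets the inputs (α = 0.048, power 0.977). This does not affect the point, because the label hangs on 12 of 16.

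**2. The limit.** 16 × 0.70 = 11.2, so 12 is the first count above 70% (12/16 = 75%). Against a true rate of 30%, P(X ≥ 12 | n = 16) = 0.00027, far stricter than a 5% test.

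**3. Does 12 of 16 show a rate above 70%?** The exact lower limit p_L solves P(X ≥ 12 | 16, p_L) = α. It is 0.516 at α = 0.05 and 0.561 at α = 0.10. At a true rate of exactly 70%, P(X ≥ 12) = 0.450, so the result is unremarkable there. To exclude 70% at one-sided 5% would take 15 of 16:

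- P(X ≥ 15 | 0.70) = 16 × 0.7¹⁵ × 0.3 + 0.7¹⁶ = 0.026.
- P(X ≥ 14 | 0.70) = 0.026 + 120 × 0.7¹⁴ × 0.3² = 0.099.

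**4. Chance of crossing the limit with no treatment effect.** The untreated rates are assumed.

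| Untreated 6-month success rate | P(≥ 12 of 16) |
|---|---|
| 30% | 0.03% |
| 40% | 0.5% |
| 45% | 1.5% |
| 50% | 3.8% |
| 55% | 8.5% |
| 60% | 16.7% |

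The error reaches 5% at an untreated rate of 51.6% and 10% at about 56%.

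**5. What the either/or rule does to an untreated rate.** Let g and t be the spontaneous improvement rates on GDE and TUS, with rescue ignored. If the two are independent, the composite rate is 1 − (1 − g)(1 − t).

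- 16.3% on each gives 30%.
- 25% on each gives 44%.
- 30% on each gives 51%.
- 40% on each gives 64%.

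Positive correlation lowers these figures. With an assumed correlation of 0.5 between the two yes/no outcomes, 30% on each gives a both-improved rate of 0.09 + 0.5 × 0.21 = 0.195. The composite is then 0.60 − 0.195 = 40.5%, and P(≥ 12 of 16) is about 0.6%. At 40% on each, both = 0.16 + 0.5 × 0.24 = 0.28 and the composite is 52%. Counting rescue surgery as failure lowers all of these further.

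**The case against.** The strongest reply is that the limit actually used is demanding. A reader might infer from an unsupported 30% null that 12 of 16 cannot support any conclusion about ALLOB, or says nothing about it once the untreated rate is 45% or more. The figures do not bear this out: the error is 1.5% at 45%, 3.8% at 50%, and within the 10% that Section 10.5.1.2 accepts up to about 56%. That part of the reply stands.

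A reader might also infer from Section 1.1.1 that these fractures would heal anyway. The sentence says only that delayed union suggests eventual healing, with no time or rate. Sections 2.4.1 and 2.6.2 select stalled fractures: unhealed at 3 to 7 months, with no progress over the last 4 weeks. The documents therefore do not establish an untreated rate above 51.6%. Correlation between GDE and TUS also weakens the independence figures. All of this stands.

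Three further replies stand in part.

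- In a Fleming plan p0 is a threshold of interest, and the plan calls 30% uninteresting. This explains the role of the number but not its value, and the word effective goes beyond a threshold of interest.
- Π in the column header may mean the observed proportion, since the Synopsis stops recruitment when success exceeds 70%. The header would then merely restate 12 of 16, and the label would still claim too much.
- Section 10.3 and much of 10.5.6 are blacked out, and the separate SAP is not in the supplied text. A source for p0 or an analysis by component may exist there, so the absence of a source is a matter of missing detail and not an error in itself.

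**Conclusion.** The point holds in a limited form. Twelve of 16 is strong evidence against a 30% rate and fair evidence against rates up to about half. It is not evidence that the rate exceeds 70%, since the one-sided 95% lower limit is 51.6%. In an uncontrolled trial it becomes evidence of a treatment effect only for a reader who accepts that untreated success on this endpoint lies below about 51.6% (one-sided 5%) or 56% (one-sided 10%). The documents neither give that rate nor rule it out.

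The binomial results are exact. The untreated rates, the independence of the components and the correlation of 0.5 are assumptions. Section 10.5.1.2 does not say whether its 10% is one- or two-sided. If it is two-sided, the 51.6% limit applies. The label in 10.5.8.3 should be brought into line with 10.5.1.2; the design itself need not change on this account.

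**What to change.** 1. In the step table of 10.5.8.3, replace the effective-if-Π > 0.70 heading with wording that matches 10.5.1.2: *worthy of further (controlled) investigation*.
2. In the interim and final reports, give the exact lower confidence limit of the success rate at the chosen error level. Describe it as the highest untreated success rate that the result rules out, so that readers can compare it with any background rate they find credible.
3. Beside the composite, show the proportions succeeding on GDE only, on TUS only and on both, unless the redacted text or the separate SAP already provides this.
4. State the basis for p0 = 0.30 in one sentence, or say that it is a judgement.

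The cost is a more modest claim and one extra table from data already collected. No added patients or visits are needed, and no clinical rule changes.

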## ALLOB-DU1 - Clinical Study Protocol

ALLOB-DU1\_CSP

V 05

Author: [name]

February 02, 2017

Pg. 103/136

- $H_0: p \leq p_0$

- $H_1: p \geq p_1$

Using  $\alpha$  = the type I error and  $\beta$  = the type II error

The tested hypotheses are as follows:

- $H_0$  : a success rate  $\leq 30\%$  is uninteresting ( $p_0=0.30$ )
- $H_1$  : a success rate of at least  $70\%$  is expected ( $p_1=0.70$ )

Using  $\alpha = 0.05$  and  $\beta = 0.20$

In the case of a two-stages Fleming plans, the study can be stopped for ineffectiveness (if the number of successes is lower than a computed limit) or for efficacy (if the number of successes is  $\geq$  a computed limit).

#### 10.5.8.3 Results of the computing

According to the 2 stages Fleming method, 20 treated patients are required (type I error rate  $\alpha$  of 5% and a statistical power of 80%). Taking into account that patients are enrolled by cohort of 4 and considering the potential heterogeneity of the population, 32 patients in total will be enrolled and treated in the study.

Step	Nb. of patients/step	Cumulated Nb. of patients	Treatment ineffective if $\Pi < 0.30$	Treatment effective if $\Pi > 0.70$
1	16 (assessable)	-	Number of successes $\leq 4$	Number of successes $\geq 12$
2	Up to 16 (assessable)	32	n.a.	n.a.

For the first 16 assessable patients, an interim analysis will be performed at the end of the 6 months follow-up (Visit #6).

The study will be prematurely stopped for:

- Safety concerns

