#### **10.7 Sample size estimation**

Using the 2 stages Fleming method, a maximum of 32 treated patients are required. Assuming a rate of 10 % of non-assessable patients, a total of 35 patients will have to be enrolled.

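### The 20 patients said to be required by Fleming at 5% and 80% power do not follow from the stated inputs (10 to 12 do), 32 is given two different origins, and the efficacy type I error is 10% in one section and 5% in another with no sidedness.

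*Combined protocol and SAP*

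**What the plan says.** - **10.5.8.2** chooses a two-stage Fleming plan with a binary success criterion. The null is a success rate of 30% or less, the alternative 70% or more, with alpha 0.05 and beta 0.20. The word one-sided does not appear, but both hypotheses point in one direction.
- **10.5.8.3** states "According to the 2 stages Fleming method, 20 treated patients are required", at a type I error "of 5% and a statistical power of 80" per cent. It then allows for enrolment in cohorts of 4 and adds: "considering the potential heterogeneity of the population, 32 patients in total will be enrolled and treated in the study". The table gives 16 assessable patients at step 1, with efficacy declared at 12 or more successes, and up to 16 more at step 2. Both step-2 limits are marked not applicable.
- **10.7** states: "Using the 2 stages Fleming method, a maximum of 32 treated patients are required".
- **10.5.1.2** states that "two sided tests will be performed at a 5% level of significance except for efficacy analyses", and that for efficacy "the type I error rate will be increased from the usual 5% to the 10% rate".

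**The concern.** Three statements about the basis of the design do not fit together.

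1. A 40-point difference between null and alternative is large, and 20 patients looks too many for 80% power.
2. The number 32 is a judgement in 10.5.8.3 and a Fleming result in 10.7.
3. The efficacy analysis has two type I error rates, and no sidedness is given for either.

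Neither patient safety nor adequate power is at stake. What is at stake is whether the printed justification can be relied on, and which level applies to the final conclusion if the trial goes to 32. With no step-2 limit printed, that level is what the final success criterion would have to come from.

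**Working it through.** **Inputs.** p0 = 0.30, p1 = 0.70, alpha = 0.05, power = 0.80 (10.5.8.2, 10.5.8.3). Alpha is taken as one-sided because the hypotheses are directional.

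**Single stage.** Declare success at r or more of n. Alpha = P(X ≥ r | n, 0.30); power = P(X ≥ r | n, 0.70), exact binomial.
- n = 9, r = 6: alpha 0.0253, power 0.730, too low.
- n = 10, r = 6: alpha 0.0473, power 0.850. This is the smallest n.
- n = 20, r = 10: alpha 0.0480, power 0.983.

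**Two stages with Fleming limits.** Let N = n1 + n2, z = 1.645 and pa = (√(N·p0) + z·√(1−p0))² / (N + z²).
- Stop for futility at stage 1 at or below round[n1·pa − z·√(N·pa(1−pa))].
- Stop for efficacy at stage 1 at or above round[n1·p0 + z·√(N·p0(1−p0))] + 1.
- Final success at or above round[N·p0 + z·√(N·p0(1−p0))] + 1.

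With a, r1 and r denoting these three limits, the chance of declaring success is P(X1 ≥ r1) + Σ P(X1 = x)·P(X2 ≥ r − x), summed over x from a+1 to r1−1. It is evaluated at 0.30 for alpha and 0.70 for power.

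For 10+10, the final limit is 20×0.30 + 1.645×√4.2 = 9.37, rounded to 9, plus 1 = 10. The other limits follow in the same way.

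| Stages | Futility ≤ | Efficacy ≥ | Final ≥ | Alpha | Power |
|---|---|---|---|---|---|
| 4+4 | 1 | 4 | 6 | 0.0166 | 0.572 |
| 5+5 | 2 | 5 | 6 | 0.0374 | 0.776 |
| 6+6 | 2 | 5 | 7 | 0.0392 | 0.859 |
| 4+8 | 0 | 5 | 7 | 0.0383 | 0.880 |
| 8+4 | 3 | 6 | 7 | 0.0389 | 0.873 |
| 8+12 | 2 | 7 | 10 | 0.0451 | 0.975 |
| 10+10 | 3 | 7 | 10 | 0.0484 | 0.977 |
| 12+8 | 4 | 8 | 10 | 0.0471 | 0.979 |

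The smallest N is therefore 12 in equal stages, and also 12 when both stages are multiples of 4. Over all splits of 20, power is 0.963 to 0.983.

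**Can 20 be recovered another way?** At 2.5% per side, a single stage needs 13 (8 or more: alpha 0.0182, power 0.835) and equal Fleming stages need 18 (9+9: 0.0198, 0.930). If both stages must also be multiples of 4, N = 12 has power of at most 0.723. N = 16 has alpha 0.0253 to 0.0263, just over the limit. N = 20 then qualifies (8+12: 0.0172, 0.947). This is the only route found on which 20 is the smallest number. The text does not describe it, and its power is about 95%, not 80%.

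**What the two alphas imply at 32.** Take the plan's 16+16 with efficacy at 12 or more at step 1. The final limits below are constructed here, since the plan prints none. They are shown for both futility limits in the plan: 4 or fewer (table in 10.5.8.3) and fewer than 4 (text of 10.5.8.3, and 2.5).

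| Final ≥ | Alpha (stop ≤4 / <4) | Power at 0.70 |
|---|---|---|
| 13/32 | 0.126 / 0.131 | 0.9996 / 0.9998 |
| 14/32 | 0.068 / 0.069 | 0.9993 / 0.9994 |
| 15/32 | 0.032 / 0.033 | 0.9981 / 0.9982 |

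One-sided 10% gives 14; one-sided 5% gives 15. The two readings disagree only at exactly 14 of 32. The chance of that result (stop ≤4 / <4) is 3.5 / 3.7% at a true rate of 0.30, 12.4 / 12.8% at 0.40, 10.6 / 10.9% at 0.50, and 0.12% at 0.70 under either limit.

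**The case against.** - **Twenty does satisfy the targets.** Its alpha can be held below 5% and its power is above 80%, so nothing is missed. That is true, but the text calls 20 the number required and ties it to 80% power. It is about twice what the printed inputs need. Cohorts of 4 are invoked only for the step from 20 to 32, so they do not explain 20.
- **The two alphas may be one.** The sentence before the 10% statement speaks of two-sided 5% tests, so the usual 5% can be read as two-sided. A two-sided 10% then equals the one-sided 5% of the Fleming section. This is a plausible reading and may be what was meant. What stands is that no visible text says it. It also cannot be combined with the 2.5%-per-side route to 20.
- **Some text is hidden or deferred.** Part of 10.5.6.1 is blacked out, and a separate SAP is named as the reference for methods. Either could supply the final limit and its sidedness. Neither would alter the 20, the 80% or the 32 printed here.
- **The 14/32 disagreement is hypothetical.** It needs the one-sided reading of 10% and a final cut-off that the plan does not print, and it is rare at the 70% alternative. It illustrates the ambiguity and is not a forecast.
- **The 32 in 10.7 is shorthand.** A reader of 10.5.8.3 can find the rationale, but the sentence in 10.7 is still incorrect as it stands.

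**Conclusion.** The concern holds. From the stated hypotheses, with alpha one-sided, the requirement is 10 patients (single stage) or 12 (Fleming limits in equal stages, or in stages of multiples of 4), against a stated 20. Power at 20 is 96 to 98%, against a stated 80%; at 2.5% per side it is still 93 to 95%. Because the stage sizes and limits behind 20 are not printed, the figure cannot be verified. Sections 10.5.8.3 and 10.7 contradict each other on where 32 comes from. The 10% and 5% error rates are a gap in wording if two-sided against one-sided was intended, and a real conflict otherwise. The trial is not underpowered on any reading: 16+16 has power of about 99.8% or more at 0.70 with a final limit of 14 or 15. This is worth correcting, but it does not threaten the conduct of the trial.

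**What to change.** 1. State one type I error for efficacy, with its sidedness, in the same words in 10.5.1.2, 10.5.8.2 and 10.5.8.3 (for example, one-sided 5%, equivalent to two-sided 10%). Derive from it the step-2 limit now marked not applicable.
2. Replace the sentence on 20 patients and 80% power in 10.5.8.3, and the Fleming sentence in 10.7, with a statement that 32 was chosen for the cohort structure and the heterogeneity of the population.
3. Reconcile the two interim futility limits, then report the exact alpha and power of 16+16. For illustration, with 12 or more at step 1 and 15 or more of 32 at the end, alpha is 0.032 (stop at 4 or fewer) or 0.033 (stop below 4). Power at 0.70 is 99.8%, and the success rate detectable with 80% power is about 0.53, in both cases.

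The cost is protocol and SAP text only; patient numbers stay as they are. The step-2 limit is a new decision rule, so it must be fixed before the final efficacy data are seen.
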